4 SUBJECT SELECTION AND WITHDRAWAL

4.1 Number of Subjects

There will be up to 150 subjects enrolled into this study, divided into two groups. There will be no protocol or procedural differences between the groups. The first group of up to 100 subjects will be used to gather data to determine the thresholds for fluid responsiveness that would be used for the second group of 50 subjects. The second group will be the validation set to be used to evaluate study objectives. The anticipated duration of subject participation in this study will not exceed 1 visit. The study enrollment period is expected to be approximately 2 years.

4.2 Inclusion Criteria

- 18-64 years of age at the time of consent
- Scheduled for elective surgery requiring general anesthesia and mechanical ventilation
- Arterial line and other standard of care line placement indicated as part of the scheduled surgical procedure

4.3 Exclusion Criteria

- Patients diagnosed with or history of heart failure, angina, pulmonary heart disease, rheumatic heart disease, cardiomyopathy, congenital heart disease, or valvular heart disease.
- Patients with surgeries at or around site of sensor placement or skin abnormalities affecting the sensor placement area such as psoriasis, eczema, angioma, scar tissue, burn, fungal infection, substantial skin breakdown, nail polish or acrylic nails that would prevent monitoring of pulse-oximeter physiological parameters during the study.
- Patients with cardiac arrhythmias
- Patients with intracardiac shunts
- Patients who live in a nursing home or long-term care facility
- Patients of all ages with underlying medical conditions, particularly if not well controlled, including
 - Patients with chronic lung disease or moderate to severe asthma
 - Patients who are immunocompromised, which may include: patients receiving cancer treatment, smoking, bone marrow or organ transplantation, immune deficiencies, poorly controlled HIV or AIDS, and prolonged use of corticosteroids and other immune weakening medications
- Patients with severe obesity body mass index [BMI] of 40 or higher
- Patients with diabetes
- Patients with chronic kidney disease undergoing dialysis
- Patients with liver disease or who have been scheduled for or have had a liver transplant

4.4 Subject Recruitment and Screening

The surgical and interventional schedule at [REDACTED] Main OR will be screened by the research team to identify the potential candidate(s). The study staff will send an email over the [REDACTED] server to the principal investigator or Co-investigator to confirm that the patient is eligible for the study. The email will not contain any PHI. Once confirmed, additional subject screening will be performed through a telephone script to reduce physical contact due to COVID-19 precautions. The study staff will provide information about the study and ask if they are interested in participating. A copy of the consent will be emailed to patients who express interest are found to be eligible for the study. If the patient does not express interest in the study during the phone call, no further communication will be made with the patient. To ensure patient privacy, phone calls to patients will occur in a private room, and screening scripts will be discarded. If the patient is interested in the study, the PI or Co-I will obtain written informed consent on the morning of the subject's surgery. The prospective subject will be given sufficient time to review the consent form and discuss the study with friends and family. A written consent form will be required from all consenting subjects.

The patient's privacy will be protected. Only the information relevant to study will be obtained. The patient's information will be kept confidential; if data is written on paper, the paper will be either kept in the research folder which is kept in the

hospital or shredded when it is not needed. If patient data is kept on a computer, the data will only be stored on hospital computers. All data will be de-identified before (1) the study team conducts any statistical tests and (2) sharing the data to Masimo Corporation. The patient's privacy will be protected such that when we approach the subject, during pre-op, we will do so when they are in a private room with or without their family so that any personal information will be kept among their family or just themselves. The Privacy of the patient will be protected throughout the study and beyond the study.

4.5 Informed Consent Process

The Investigator(s) and/or staff delegated for this task are responsible for conducting the informed consent process and for obtaining written informed consent and the HIPAA/data protection authorization from each potential subject before any study-specific procedures required by the clinical protocol are performed.

Informed consent should be obtained in written format and using a form approved by the local IRB and Sponsor. Written (signed) informed consent will be obtained from subjects or their legally authorized representative (LAR). After a patient is deemed eligible from the screening process using the [REDACTED] surgical schedule, study team members will call the prospective subject to explain the study the day before their scheduled surgical procedure. A copy of the consent will be emailed to the patients who express interest to allow adequate time to review the consent and consider their participation. On the morning of their surgery, the PI or Co-I will provide the consent form in-person. They will give the prospective subject additional time to review the consent form, discuss the study with family, and ask questions. If the subject is interested in participating in the study, written consent will be obtained on the day of the surgical procedure. In addition to the full disclosure of the risks and benefits of participating in the study, patients will be informed that their participation is voluntary and their decision will not impact patient care. They will also be given adequate time to ask questions regarding the study and to discuss with family and friends before making the decision.

All signed consent and HIPAA forms will be kept [REDACTED] and are only accessible to study team members [REDACTED]. If the patient refuses to participate, we will not enroll the patient in this study. The original signed consent should be filed in the hospital/clinical chart or with the subject's study documents. A signed copy of the consent and HIPAA/data protection authorization must be provided to the subject. The Principal Investigator (PI) is responsible for ensuring any new information related to the study will be provided to the subject and/or subject's LAR. Subject may need to be re-consented to continue participation, if required by the IRB.

The English version of the consent form will be translated into appropriate languages for non-English speaking subjects once IRB approval is granted. An interpreter will be involved in the consenting process. **Note:** The IRB must officially stamp the translated consent forms.

4.6 Subject Withdrawal

All enrolled subjects have the right to withdraw their consent at any time during this study. All data collected until the time of subject withdrawal will remain in the study database and will be used for analysis. If a subject is withdrawn from the study, the reason for withdrawal will be recorded in the CRF and in the subject's hospital record.

4.7 Subject Discontinuation by Investigator

An Investigator may discontinue a subject from the study, with or without the subject's consent for any reason that may, in the Investigator's opinion, negatively affect the well-being of the subject, subject non-compliance, Sponsor instruction, or if the IRB stops the study for any reason. If a subject is discontinued from the study, the Investigator will promptly inform the subject and Sponsor. The reason for discontinuation will be recorded in the CRF and in the subject's hospital record.

5 RISKS AND BENEFITS

The major risks to the patient are related to the surgical procedure (bleeding, infection, pain, etc.). Participation in this protocol places the patient at minimal if any additional risk. There is theoretical extremely small risk of damage to the subject's fingers from the device including potential temporary redness or skin irritation or discomfort associated with exposure to the sensor.

There is no intervention and no alteration to the patient's surgical procedure. Patient will receive standard patient care. All additional measurements will be done through non-invasive sensors. None of the data recorded through these sensors will be used to make decisions regarding the patient.

Noninvasive measurement with Masimo Corporation Radical 7 pulse oximetry: The risk is minimal since the measurement is noninvasive and uses optical technology similar to conventional pulse oximetry.

Sensor risks: As with all optical sensors, the device has the risk of thermal burn. The design includes safeguards, and this risk is believed to be low. All patient-contact materials, including the adhesive used in the design of the Masimo Rainbow sensors, have been subjected to biocompatibility tests per ISO 10993-1 and results demonstrate that the materials are non-toxic, non-irritating, and non-sensitizing. The sensors have been subjected to performance, mechanical, and electrical testing and results demonstrate that the sensors meet the requirements for safety and effectiveness for the intended use of the product. Pressure damage may occur to the tissue if the sensor is placed too tightly.

Volume expansion risks: Risks of volume expansion with [REDACTED] can include fluid accumulation in the lungs or tissue, decreased oxygen saturation, and edema.

There will be no direct benefits to the enrolled patients. Future benefits to patients might include a reduction in invasive procedures due to the ability to trend moment-by-moment physiological parameters.

6 STUDY DEVICES

6.1 Investigational Devices

Masimo investigational pulse CO-oximeter devices and/or sensors with the RPVi parameter, are with the same or similar technology and materials as the Masimo FDA cleared devices and sensors, that pose no additional risk to human subjects than the FDA cleared devices and sensors.

- Masimo Radical 7 Rainbow monitoring device
- Masimo Root Patient Monitoring and Connectivity Platform
- Masimo Rainbow disposable sensor(s) (FDA cleared or investigational devices)

6.2 FDA-Cleared Devices

- FDA cleared hemodynamic monitor(s) (i.e., Edwards Vigileo/FloTrac or Philips IntelliVue)
- Laptop with [REDACTED] software
- Electronic data collection of high speed arterial line waveforms

6.3 Device Accountability

6.3.1 Receipt of Study Device

Masimo may ship or hand-carry devices and sensors to the investigative sites. Upon receipt of the study device supplies, an inventory must be performed and the device accountability log filled out and signed by the person accepting the shipment. It is important that the designated study staff counts and verifies that the shipment contains all the items noted in the shipment inventory. Any damaged or unusable study devices in a given shipment will be documented in the study files. The investigator must notify the study sponsor of any damaged or unusable study devices that were supplied to the investigator's site.

6.3.2 Use of Study Device

Use of devices and sensors will be documented on case report forms for each subject.

6.3.3 Return or Destruction of Study Device

At the completion of the study, there will be a final reconciliation of study devices and sensors shipped, devices/sensors used, and devices/sensors remaining. This reconciliation will be logged on the device accountability log. Any discrepancies noted will be investigated, resolved, and documented prior to return or destruction of unused study devices. Devices destroyed on site will only be upon written instruction from the sponsor and will be documented in the study files.

6.3.4 Device Deficiency

Device deficiency is defined as inadequacy of a medical device with respect to its identity, quality, durability, reliability, safety or performance. Device deficiencies include malfunctions, use errors, and inadequate labeling. (ISO 14155:2011 3.15). All Masimo device related deficiencies should be reported to the Sponsor and must be recorded in the CRF in a timely manner. This excludes computer issues. These should be reported to the IRB as required per local requirements. When a Masimo device deficiency is observed, every effort should be made to return the device and its packaging to the Sponsor in a timely manner.

7 STUDY PROCEDURES

- Patients are assigned to be ventilated in a volume controlled mode with a tidal volume of either 6 or 8 $\text{ml} \cdot \text{kg}^{-1}$ of ideal body weight (Devine formula) at a frequency [REDACTED]. Positive end-expiratory pressure is to be set [REDACTED] according to the attending physician.
- Anesthesia is induced as per standard of care. Radial and pulmonary arterial catheters inserted as per standard of care.
- All required sensors are placed as per the corresponding instructions for use for the various measurements
- All patients are to be studied [REDACTED] with no changes in anaesthetic protocol and no volume expansion. Unless clinically contraindicated, patients will receive an intravenous volume expansion consisting of [REDACTED] given over [REDACTED].
- Baseline set of haemodynamic measurements (stroke volume and or cardiac output) are to be performed prior to the intravenous volume expansion.
- A repeat set of hemodynamic measurements are to be performed [REDACTED] after volume expansion.

8 STATISTICAL PLAN

Prior studies of the predictive abilities of dynamic monitors of cardiac function with respect to cardiac output have established that sample sizes of 50 patients are sufficient to characterize the performance of the monitor. However, based on an ongoing Masimo study at another clinical test site, preliminary data received suggests that, of the first 83 subjects enrolled approximately 29% were responders. Therefore, in order to analyze the ability of RPVi, the sample size will be increased to a total of up to 150 patients. The first group of up to 100 subjects will be used to gather data to determine the thresholds for fluid responsiveness that would be used for the second group of 50 subjects. The second group will be the validation set to be used to evaluate study objectives in **section 2.1**. As such, the study will be registered on ClinicalTrials.gov but only results from the validation phase will be posted.

Normality of distribution will be tested before any statistical evaluation by using the Kolmogorov- Smirnov method. Descriptive statistical data will be reported as mean \pm SD. Except for the bias between both methods (RPVi vs PPV/SVV and SV/CO measurements). Comparisons between PPV/SVV and RPVi and between CO/SV measurements will be performed with a paired student t test. PPV/SVV and RPVi as well as SV/CO measurements will be compared using Bland and Altman. In order to evaluate the ability of RPVi to reliably detect changes in PPV/SVV and for CO measurements to accurately track Flotrac CO changes we will use a method based on polar plotting of PPV/SVV and RPVi and CO measurements changes over consecutive cycles as described by Critchley et al. We will exclude from this analysis small changes of mean value of

PPV/SVV and RPVi and CO measurements less than 3%. In this method, a good trending ability requires an angular bias no greater than ± 5 degrees and a SD for the polar angle of less than ± 15 degrees. In this method, simultaneous changes of each indices of consecutive validated respiratory cycle will be reported on a polar plot. The polar angle will be derived from the ratio of the changes of the two indices such a ratio close to one led to a null angle with the x axis, this angle approach a 90 degrees angle when the ratio diverges from one. The radius will be the mean of the simultaneous changes of the two indices between two consecutive validated respiratory cycles. In these conditions a mean angle and its SD can be calculated.

The strength of linear dependence between PPV/SVV and RPVi and SV/CO measurements for all patients will be measured by the Pearson coefficient of correlation. The mean of correlation coefficients and comparison between correlation coefficients will be performed after a Fischer's transformation. In order to analyze the ability of RPVi to correctly classify the respiratory cycle as responder or non-responder after a volume loading in respect to a theoretical threshold value of PPV/SVV of 12%, we will measure the area under the curve of a Receiver Operating Characteristic (ROC) curve. Then the selected value of RPVi for each patient will be the one which maximized the Youden index (sensitivity + (specificity - 1)). The agreement between the two classifications will be quantified by the Kappa score for each patient, taking as threshold value of RPVi the individual value determined by the ROC curve. The reported mean values of areas under ROC curves and Kappa scores will be therefore calculated from the individual values. Taking the intra patients coefficient of correlation as a dependent variable, we will estimate its relationship with potentially explanatory variables by using univariate analysis, including Student t test for qualitative data and correlation for quantitative data and multivariate analysis by multiple linear regression. Categorical binary variable will be transformed into dummy variables. Other correlations will be evaluated by Pearson coefficient.

For all comparisons, a P value < 0.05 will be considered significant. Statistical analysis will be performed using SPSS software version 13.0 for Windows (SPSS Inc., Chicago, IL).

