9.3 Adverse Event Reporting

The PI must promptly report the following adverse events to the Sponsor through the CRF and Adverse Event Report Form, and follow their IRB policy for safety event reporting:

- All Adverse Events, both anticipated and unanticipated and both serious and non-serious, after the first Masimo sensor is placed and up to the last Masimo sensor is removed
- All Unanticipated Adverse Device Effects after the first Masimo sensor is placed and up to the last Masimo sensor is removed

SAEs and UADEs must be reported to the Sponsor within 48 hours. All other Adverse Events should be reported to the Sponsor within 5 business days.

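### The validation-only posting rule makes no exception for adverse events, so read literally it would leave up to 100 of up to 150 subjects out of the posted safety record

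*Combined protocol and SAP*

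**What the plan says.** Section 4.1 sets the size and the split: "There will be up to 150 subjects enrolled into this study, divided into two groups". Section 8 gives the first group its role: "The first group of up to 100 subjects will be used to gather data to determine the thresholds for fluid responsiveness". Section 4.1 gives the role of the other 50: "The second group will be the validation set to be used to evaluate study objectives". Section 8 then draws a consequence for reporting: "the study will be registered on ClinicalTrials.gov but only results from the validation phase will be posted".

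The two groups do not differ in what is done to them. Section 4.1 says: "There will be no protocol or procedural differences between the groups". Section 7 plans the fluid load without regard to group: "Unless clinically contraindicated, patients will receive an intravenous volume expansion consisting of" a fluid whose details are redacted. Section 5 lists thermal burn and pressure damage as sensor risks, and says that volume expansion "can include fluid accumulation in the lungs or tissue, decreased oxygen saturation, and edema".

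Safety data are collected without regard to group. Under section 9.3 the investigator reports to the Sponsor "All Adverse Events, both anticipated and unanticipated and both serious and non-serious, after the first Masimo sensor is placed", until the last sensor is removed, and follows IRB policy. Section 10.4 puts adverse events and device deficiencies on the case report form.

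The analyses in section 8 are t tests, Bland-Altman, polar plots, correlation, ROC, kappa and regression. The section defines no safety set and no adverse-event table. Section 9 covers the reporting of individual events and names no aggregate or public summary.

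**The concern.** A hold-out set protects a performance estimate from optimism: a threshold chosen in one set of patients will look too good if it is tested in the same patients. That is a proper reason to report RPVi classification performance from the second group alone. Adverse events have no threshold to tune. A skin burn or a fall in oxygen saturation in a first-group subject is as informative about harm as the same event in a second-group subject.

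The posting sentence does not separate these two kinds of result. If it is followed as written, the public safety table would rest on the 50 validation subjects. It could show no events of a given kind when such events had occurred among the other subjects, who had the same planned exposure. Because section 8 plans no adverse-event summary for any set of subjects, nothing else in the analysis plan fills the gap.

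What is at stake is the completeness of the posted record. The validity of the RPVi analyses and the protection of subjects during the study are not in question.

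**Working it through.** **Inputs from the documents.** First group: up to 100 (sections 4.1 and 8). Validation group: 50 (sections 4.1 and 8). Total: up to 150 (sections 4.1 and 8). Planned procedures: the same in both groups (section 4.1).

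**Input not in the documents.** No adverse-event rate is given. Per-subject risks p of 0.5%, 1%, 2% and 5% are assumed below. Subjects are taken as independent, with the same risk in both groups.

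**Step 1: the plan's own total.** 100 + 50 = 150, as stated. The share outside the posted set is 100/150 = 66.7% and the share inside is 50/150 = 33.3%. With equal risk, about two thirds of affected subjects would be expected to fall outside the posted set, whatever the rate.

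**Step 2: what a posted zero would exclude.** With no events in n subjects, the exact one-sided 95% upper bound is 1 − 0.05^(1/n).

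- n = 50: 1 − 0.05^(1/50) = 5.8%
- n = 150: 1 − 0.05^(1/150) = 2.0%

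**Step 3: chance that at least one affected subject is seen.** This is 1 − (1 − p)^n.

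| Assumed p | n = 50 | n = 100 | n = 150 |
|---|---|---|---|
| 0.5% | 22.2% | 39.4% | 52.9% |
| 1% | 39.5% | 63.4% | 77.9% |
| 2% | 63.6% | 86.7% | 95.2% |
| 5% | 92.3% | 99.4% | 99.9% |

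**Step 4: chance that the posted record is clean although the study is not.** None of the 50 is affected and at least one of the 100 is: (1 − p)^50 × [1 − (1 − p)^100].

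- p = 0.5%: (1 − 0.2217) × 0.3942 = 0.307, or 31%
- p = 1%: (1 − 0.3950) × 0.6340 = 0.384, or 38%
- p = 2%: (1 − 0.6358) × 0.8674 = 0.316, or 32%
- p = 5%: (1 − 0.9231) × 0.9941 = 0.076, or 8%

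**Step 5: effect of the ceiling.** The second factor grows with the size of the first group, so the figures in step 4 are maxima. If only 50 subjects were enrolled in the first group, for illustration, the value at p = 1% would be 0.605 × 0.395 = 0.239, or 24%.

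**The case against.** The strongest reply is that the sentence was never meant to cover safety. It is introduced as a consequence of the validation set's role in evaluating the objectives of section 2.1. Those objectives concern RPVi as a predictor and its comparison with PPV and SVV, and safety is not among them. In that context, results can naturally mean performance results. This stands as a possible reading. A reader might infer that the plan decides to withhold first-group adverse events, and the documents do not support that. They support only that the rule is unqualified and that no other text preserves those events for posting.

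The second reply is that oversight covers everyone. All events from sensor placement to removal go to the Sponsor, serious adverse events and unanticipated adverse device effects within 48 hours, and IRB policy applies (section 9.3). Monitors check the documentation of serious events (section 11.5). An unanticipated device effect that presents an unreasonable risk can end the study (section 12.4). This stands in full, so it would be wrong to infer that first-group subjects go unmonitored.

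The third reply is that the numbers depend on an assumed rate. This also stands, which is why a range is shown. Section 9.1 counts any untoward occurrence, device-related or not. The rate for all events together could therefore be high enough that a wholly empty posted table is unlikely. The small assumed risks are more relevant to a specific, uncommon harm.

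Two further inferences are tempting and should not be made. One is that a 50-subject record undermines the minimal-risk statement in section 5. That statement is a prospective assessment. For the sensors it draws on the optical technology, biocompatibility testing and bench testing, and the plan does not say that posted results will support it. The other is that a safety comparison of the two tidal volumes is lost. Section 2.1 describes a nonrandomized study, and no such comparison is planned.

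**Conclusion.** The point holds as a gap between an unqualified posting rule and a rationale that covers only RPVi performance. Applied literally, the rule would omit the adverse events of up to 100 of up to 150 subjects from the posted record. The bound that a zero count supports would be 5.8%, where the full study could give 2.0%. Over the assumed risks of 0.5% to 2%, there is roughly a one-in-three chance that a harm occurs in the study and is absent from the posted 50. At 5% the chance falls to 8%.

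These figures rest on a full first group of 100, independent subjects and equal risk in both groups. Exposure is equal by plan only, since the volume expansion can be withheld when clinically contraindicated. The text between sections 2.1 and 4 was not available to check. The performance-only reading remains open. If that is what the sponsor intends, the sentence should say so. The conclusion does not extend to the conduct of the study, the choice of validation set or any RPVi estimate.

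**What to change.** In section 8, limit the posting sentence to RPVi performance results, so that the hold-out principle stays intact for the aims it serves. Then add wording to this effect: *Adverse events, adverse device effects and device deficiencies will be summarised and posted for every subject in whom a Masimo sensor was placed, in both groups.* A breakdown by assigned tidal volume is optional and would be descriptive only.

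The cost is one amended sentence, one added sentence and one table. The adverse-event and device-deficiency data are already required on the case report form (sections 6.3.4, 9.3 and 10.4). Sample size, validation design and procedures do not change. The downside is a longer posted adverse-event table.

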The evolution of the pulse oximetry sensors to incorporate multi-wavelength technologies provided the opportunity to modify the PVi algorithm and improve clinical performance. As a dynamic monitor of cardiac function, PVi/ RPVi is analogous to pulse pressure variation (PPV), which may be derived through minimally-invasive means using beat-to-beat arterial pressure expressed as a percentage by the Philips IntelliVue (Philips Labs, Noord Brabant, NL) or stroke volume variation (SVV), which may be derived through minimally-invasive means using pulse contour analysis of the arterial pressure waveform as done by the Vigileo/Flotrac System (Edwards Labs, Irvine, CA) or Philips IntelliVue (Philips Labs, Noord Brabant, NL). Multiple studies have demonstrated that PPV and/or SVV is a valuable tool in predicting fluid responsiveness in mechanically ventilated patients.

The aim of this study is to test the ability of RPVi to predict fluid responsiveness in mechanically ventilated patients in the operating room and to compare it to other dynamic monitors of cardiac function in this setting.

This study will include patients [REDACTED] undergoing cardiac surgical procedures in which pulmonary and peripheral arterial catheters are standard monitors used for continuous monitoring of cardiac function and blood pressure, respectively. Patients with cardiac arrhythmias and intracardiac shunts will be excluded. Patients will be assigned to one of the two study groups with different tidal volumes: 6 ml/kg IBW and 8 ml/kg IBW. Both tidal volumes are within the range that is commonly used intra-operatively. In patients without significant pulmonary disease there is no significant risk or benefit associated with either tidal volume, however, there is evidence of decreased utility of the dynamic monitors of cardiac function (PPV/SVV) at lower tidal volumes. Attention to the tidal volume will aid the assessment of the utility of RPVi as a monitor of cardiac response to fluid administration.

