2 STUDY OBJECTIVES

2.1 Primary Objective

This is a prospective, nonrandomized, sequential data collection study to evaluate the ability of RPVi to predict fluid responsiveness in comparison with other dynamic parameters including SVV and/or PPV. Although this is a non-interventional study, focused on data collection, patients will be assigned to one of the two study groups with different tidal volumes: 6 ml/kg IBW and 8 ml/kg IBW. The research data will not be used to modify the subject's standard of care.

Specific aims:

- Evaluate the clinical utility of the RPVi as a predictor of fluid responsiveness in mechanically ventilated patients at two specific tidal volumes (6 ml/kg IBW and 8 ml/kg IBW).
- Characterize the correlations between the RPVi and PPV and/or SVV, as measured by FDA cleared comparator systems, as predictors of fluid responsiveness at two specific tidal volumes (6 ml/kg IBW and 8 ml/kg IBW).

Hypothesis (constructed as the null):

- RPVi as a dynamic monitor of cardiac function will not predict a subsequent increase in cardiac output following the administration of a fluid bolus of a crystalloid solution at a tidal volume of either 6 or 8 ml/kg IBW in intubated, mechanically ventilated patients.

- Changes in RPVi will not differ from concurrent changes in PPV and/or SVV, as measured by FDA cleared comparator systems following the administration of a fluid bolus of a crystalloid solution at a tidal volume of either 6 or 8 ml/kg IBW in intubated, mechanically ventilated patients.

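### Hypothesis 2 concerns the difference between the changes in RPVi and in PPV/SVV across the bolus, but no analysis in section 8 is defined on that quantity

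*Combined protocol and SAP*

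**What the plan says.** Section 2.1 lists two hypotheses, both written as nulls. The second is that "Changes in RPVi will not differ from concurrent changes in PPV and/or SVV", with the setting given as "following the administration of a fluid bolus of a crystalloid solution at a tidal volume of either 6 or 8 ml/kg IBW". A separate specific aim is to "Characterize the correlations between the RPVi and PPV and/or SVV". Sections 4.1 and 8 say that the 50-subject validation group will be used to evaluate the objectives.

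Section 8 offers these analyses of RPVi against PPV/SVV:

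- A paired t test: "Comparisons between PPV/SVV and RPVi and between CO/SV measurements will be performed with a paired student t test".
- Agreement: "PPV/SVV and RPVi as well as SV/CO measurements will be compared using Bland and Altman".
- A polar plot of changes from one validated respiratory cycle to the next. Changes under 3% are excluded, and the criteria are an angular bias within 5 degrees and an SD of the angle below 15 degrees.
- Pearson correlations.
- ROC, Youden and Kappa classification of respiratory cycles against a PPV/SVV threshold of 12%.

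All comparisons are tested at P < 0.05. In section 7 the measurement step reads "Baseline set of haemodynamic measurements (stroke volume and or cardiac output) are to be performed prior to the intravenous volume expansion", followed by a repeat set after the volume expansion.

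**The concern.** A hypothesis about changes needs an analysis variable that is a change. The sentences on the t test and on Bland-Altman name the indices themselves, so their plain reading is a comparison of levels, and they do not say whether at baseline, after the bolus or averaged over both.

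Levels and changes answer different questions. Suppose RPVi reads a fixed amount above PPV in every patient and both fall equally after the bolus. Hypothesis 2 is then true, yet a test on levels tends to reject it. Suppose instead that the indices match at baseline and respond differently to fluid. Hypothesis 2 is then false, and a test on baseline levels has nothing to find. What is at stake is the answer to one of the two stated hypotheses: with the choice left open, the same 50 patients can give opposite conclusions.

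**Working it through.** **1. Match each analysis to the hypothesis 2 quantity.** Write D = (post minus pre RPVi) minus (post minus pre PPV, or SVV) for each patient. Hypothesis 2 says that the mean of D is zero.

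| Section 8 analysis | Uses changes? | Across the bolus? | Estimates mean D? |
|---|---|---|---|
| Paired t test | not stated | not stated | only if run on changes |
| Bland-Altman | not stated | not stated | only if run on changes |
| Polar plot | yes | no, cycle to cycle | no, it summarises a ratio as an angle |
| Pearson | not stated | not stated | no, it is blind to an offset or a difference in mean change |
| ROC, Youden, Kappa | no | volume loading is mentioned, but cycles are classified | no |

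No row is defined on D.

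**2. Size of the level-versus-change problem.** The plan gives no SD, effect size or power for hypothesis 2, so it has no figure of its own to reproduce. The illustration below rests on assumptions:

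- n = 50 (section 8) and alpha 0.05 (section 8), taken as two-sided.
- B = baseline RPVi minus baseline PPV/SVV; D as above.
- B and D are independent, each with SD 1. These values are not in the documents.

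The post-bolus level difference is B + D, with SD √2 = 1.414. The average of the two level differences is B + D/2, with SD √1.25 = 1.118. The standardised effect is the mean divided by the SD, and power comes from the noncentral t with 49 degrees of freedom and noncentrality effect × √50.

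- Mean B 0.5, mean D 0: effects 0.5, 0.5/1.414 = 0.354, 0.5/1.118 = 0.447 and 0.
- Mean B 0, mean D 0.5: effects 0, 0.354, 0.25/1.118 = 0.224 and 0.5.
- Mean B −0.5, mean D 0.5: effects −0.5, 0, −0.224 and 0.5.

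Percent of trials significant:

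| Truth | Baseline levels | Post-bolus levels | Average of both | Changes (D) |
|---|---|---|---|---|
| Offset 0.5, equal changes | 93 | 69 | 87 | 5 |
| No offset, changes differ by 0.5 | 5 | 69 | 34 | 93 |
| Offset −0.5, changes differ by 0.5 | 93 | 5 | 34 | 93 |

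In the first row hypothesis 2 is true, and every version on levels rejects it far more often than 5%. In the second and third rows it is false, and only the test on D detects this reliably. The 93 on baseline levels in the third row reflects the offset, which has the opposite sign to the difference in change.

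**3. What a non-significant result would carry.** With the correct variable, in units of the SD of D:

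- The chance of missing a true difference of 0.3 SD is 45% with 50 pairs and 70% with 25.
- The 95% CI half-width of the mean is t/√n: 2.010/√50 = 0.28 SD with 50 pairs, and 2.064/√25 = 0.41 SD with 25.
- The CI half-width of each limit of agreement is t × √(1/n + 1.96²/(2(n−1))): 0.49 SD with 50 pairs and 0.72 SD with 25.

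The figure of 25 assumes an even tidal-volume split in the validation set. The documents give no split.

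**The case against.** The best defence is that section 8 assigns the validation set to the section 2.1 objectives, and section 2.1 already names changes, so an analyst would naturally run the paired test on changes. That is reasonable, and it means the plan is not committed to the wrong quantity. But the sentence does not say so, and section 8 does use the word changes where it means them, in the polar plot. The choice should not be left until the data are in hand.

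A second defence is that the polar plot deals with changes and has its own pass criteria. Both are true, so a reader who concluded that P < 0.05 is the only decision rule in section 8 would be wrong. The criteria govern cycle-to-cycle trending, however. They do not govern the t test and do not estimate the difference in change across the bolus.

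Two stronger readings are tempting and are not supported:

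- A reader might infer that the sponsor will take a non-significant t test as agreement. The plan never says this, and it has Bland-Altman and the polar plot for agreement and trending. The miss rates are a caution only.
- A reader might infer from section 7 that RPVi and PPV/SVV are not recorded at both times, because only stroke volume and cardiac output are named. That naming is attached to the baseline set alone, part of the timing is redacted, and section 10.5 has device data and arterial waveforms uploaded. The values are probably available.

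**Conclusion.** The concern holds as a mismatch between hypothesis and analysis. Hypothesis 2 is about a difference in changes across the bolus, and section 8 defines no analysis on it. This is more than missing detail, because the literal reading tests a level offset and can give the wrong answer in either direction. The mismatch itself is textual and rests on no assumed number. Its size does: the 93% against 5% contrast depends on the assumed SDs, independence and 0.5 SD effects, and it shrinks for some choices of level (69% for post-bolus levels in the first two scenarios). Hypothesis 1, on predicting the cardiac output response, is not touched. The point should be put right before the validation set is analysed.

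**What to change.** Hypothesis 2 can stay as worded. In section 8, add that for hypothesis 2 the paired t test and Bland-Altman use, per patient, D = (post minus pre RPVi) minus (post minus pre PPV), and separately the same with SVV. Both indices are to be taken at the baseline and repeat measurement times of section 7. Fix one scale, percentage points: section 1.1 defines RPVi as a percentage and describes PPV as "beat-to-beat arterial pressure expressed as a percentage", and section 8 sets the PPV/SVV threshold as a percentage.

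Report mean D with its 95% CI, and the limits of agreement with their CIs, overall and by tidal volume. Give the number of complete pairs, since section 7 makes the bolus conditional ("Unless clinically contraindicated, patients will receive an intravenous volume expansion consisting of"). Interpret hypothesis 2 from the CI and not from P ≥ 0.05. Keep Pearson for the correlation aim and the polar plot for trending.

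The cost is a few sentences and no added patients. The downside is that the CIs by tidal volume will be wide (about 0.41 SD either side with 25 pairs), and the agreement result may look less favourable.
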